#### 1.4.3.3 Risks related to combined administration of BI 894416 and rifampicin

##### Potential effects of BI 894416 on rifampicin pharmacokinetics and side effects

The last dose of rifampicin will be given 14 hours prior to BI 894416 in period 2. In this trial, no relevant effect of BI 894416 on rifampicin pharmacokinetics or side effects is expected.

##### Expected effects of rifampicin on BI 894416 pharmacokinetics and side effects

It is expected that BI 894416 plasma concentrations decrease when given following a 1-week treatment with rifampicin. This is not expected to increase the risk of side effects of BI 894416.

#### 1.4.3.4 Drug-induced liver injury

Although rare, a potential for drug-induced liver injury (DILI) is under constant surveillance by sponsors and regulators. Therefore, this trial requires timely detection, evaluation, and follow-up of laboratory alterations in selected liver laboratory parameters to ensure subjects' safety; see also Section 5.2.6.1.4, adverse events of special interest.

#### **1.4.4 Overall assessment of benefit-risk ratio**

BI 894416 is a highly specific SYK inhibitor that has been adequately characterised in pre-clinical studies. The non-clinical safety package supports administration of BI 894416 for up to 4 weeks duration to men.

Data of previous trial 1371-0001 indicate good safety and tolerability of single oral doses of BI 894416 at all dose levels, i.e. up to 70 mg. In addition, data from oral administration of three SYK inhibitors are available and provide additional information on safety and tolerability of this class of drug in man. Published data indicate acceptable safety and tolerability of these three SYK inhibitors in healthy volunteers (see IB [[c03536505-04](#)]).

BI 894416 plasma exposures in the current trial are expected to be within plasma exposure values that were observed in previous first-in-man trial 1371-0001 and that were associated with good safety and tolerability.

Rifampicin is a recommended inducer of CYP3A in clinical trials and has been used successfully and safely in previous clinical trials in healthy volunteers. The drug has a potential for hepatotoxicity, which is however accounted for by stringent exclusion criteria, liver enzyme measurement as part of safety laboratory examinations and stopping criteria for the individual subject.

## **2. TRIAL OBJECTIVES AND ENDPOINTS**

### **2.1 MAIN OBJECTIVES, PRIMARY AND SECONDARY ENDPOINTS**

#### **2.1.1 Main objectives**

The main objective of this trial is to investigate the effect of rifampicin on the pharmacokinetics of BI 894416.

#### **2.1.2 Primary endpoints**

The following pharmacokinetic parameters will be determined for BI 894416:

- $AUC_{0-\infty}$  (area under the concentration-time curve of the analyte in plasma over the time interval from 0 extrapolated to infinity)
- $C_{\max}$  (maximum measured concentration of the analyte in plasma)

#### **2.1.3 Secondary endpoint**

The following pharmacokinetic parameter will be determined for BI 894416:

- $AUC_{0-tz}$  (area under the concentration-time curve of the analyte in plasma over the time interval from 0 to the last quantifiable data point)

### 3. DESCRIPTION OF DESIGN AND TRIAL POPULATION

#### 3.1 OVERALL TRIAL DESIGN AND PLAN

The study will be performed as an open-label, two-treatment, two-period, one-way crossover trial in healthy male subjects in order to compare the test treatment (T) to the reference treatment (R). The treatments will be one oral single dose of 50 mg BI 894416 as tablet formulation (tablet strength: 25 mg) following 7 days of pre-treatment with 600 mg rifampicin q.d. as tablet formulation (tablet strength: 600 mg) (T) and one oral single dose of 50 mg BI 894416 as tablet formulation (tablet strength: 25 mg) given alone (R). In both treatments, BI 894416 is administered in the fasting state. In the first treatment period (Period 1, Visit 2), all subjects are planned to undergo treatment R, and in the second treatment period (Period 2, Visit 3), all subjects are planned to undergo treatment T. For details, refer to Section [4.1](#).

There will be a washout period of at least 10 days between the administrations of BI 894416.

Based on the good safety and tolerability of BI 894416 in trial 1371-0001, the acceptable safety and tolerability of rifampicin in healthy volunteers and the fact that a decrease of BI 894416 exposure is expected when given together with the CYP and P-glycoprotein inducer rifampicin, it is acceptable to treat all subjects entered in this trial in a single cohort, i.e. with Day 1 of each treatment period on the same calendar day.

An overview of all relevant trial activities is provided in the [Flow Chart](#). For visit schedule and details of trial procedures at selected visits, refer to Sections [6.1](#) and [6.2](#), respectively.

#### 3.2 DISCUSSION OF TRIAL DESIGN, INCLUDING THE CHOICE OF CONTROL GROUP

For relative bioavailability trials, the crossover design is preferred because of its efficiency: since each subject serves as his own control, the comparison between treatments is based on an intra-subject comparison, thus removing inter-subject variability from the comparison between treatments [\[R94-1529\]](#).

Considering the potentially long-lasting induction effect of rifampicin with regards to CYP enzymes, and in order to avoid carry-over effects of rifampicin-induced induction, a one-way crossover design was selected, with administration of rifampicin in the second treatment period only. This design is not expected to lead to systematic errors in the estimation of the treatment effects since nonspecific time effects are unlikely due to the short trial duration.

Due to short half-life of BI 894416 and the sustained induction effect of rifampicin, rifampicin is not administered on Day 1 of period 2.

The open-label treatment is not expected to bias results, since the primary and secondary study endpoints are derived from measurement of plasma concentrations of the analyte. These endpoints are not expected to be affected by knowledge of treatment.

### **3.3 SELECTION OF TRIAL POPULATION**

It is planned that 16 healthy male subjects will enter the study. They will be recruited from the volunteers' pool of the trial site.

Only male subjects will be included in the study because no data on reproductive toxicology are available at this time and because, until availability of data from the 26-week Tg.rash2 carcinogenicity study, study populations are restricted to male volunteers or patients (see IB [[c03536505-04](#)]).

A log of all subjects enrolled into the trial (i.e. who have signed informed consent) will be maintained in the ISF irrespective of whether they have been treated with investigational drug or not.

#### **3.3.1 Main diagnosis for trial entry**

The study will be performed in healthy subjects.

#### **3.3.2 Inclusion criteria**

Subjects will only be included in the trial if they meet the following criteria:

1. Healthy male subjects according to the assessment of the investigator, as based on a complete medical history including a physical examination, vital signs (BP, PR), 12-lead ECG, and clinical laboratory tests
2. Age of 18 to 50 years (inclusive)
3. BMI of 18.5 to 29.9 kg/m^2 (inclusive)
4. Signed and dated written informed consent prior to admission to the study, in accordance with GCP and local legislation

#### **3.3.3 Exclusion criteria**

Subjects will not be allowed to participate, if any of the following general criteria apply:

1. Any finding in the medical examination (including BP, PR or ECG and including the neurological examination) deviating from normal and assessed as clinically relevant by the investigator
2. Repeated measurement of systolic blood pressure outside the range of 90 to 140 mmHg, diastolic blood pressure outside the range of 50 to 90 mmHg, or pulse rate outside the range of 45 to 90 bpm
3. Any laboratory value outside the reference range that the investigator considers to be of clinical relevance
4. Any evidence of a concomitant disease assessed as clinically relevant by the investigator
5. Gastrointestinal, hepatic, renal, respiratory, cardiovascular, metabolic, immunological or hormonal disorders
6. Cholecystectomy or other surgery of the gastrointestinal tract that could interfere with the pharmacokinetics of the trial medication (except appendectomy or simple hernia repair)

Proprietary confidential information © 2019 Boehringer Ingelheim International GmbH or one or more of its affiliated companies

7. Diseases of the central nervous system (including but not limited to any kind of seizures or stroke), and other relevant neurological or psychiatric disorders
8. History of relevant orthostatic hypotension, fainting spells, or blackouts
9. Chronic or relevant acute infections
10. History of relevant allergy or hypersensitivity (including allergy to the trial medication or its excipients)
11. Use of drugs within 30 days of planned administration of trial medication that might reasonably influence the results of the trial (including drugs that cause QT/QTc interval prolongation)
12. Intake of an investigational drug in another clinical trial within 60 days of planned administration of investigational drug in the current trial, or concurrent participation in another clinical trial in which investigational drug is administered
13. Smoker (unless the subject quit smoking for at least 3 months prior to first planned administration of trial medication)
14. Alcohol abuse (consumption of more than 24 g per day)
15. Drug abuse or positive drug screening
16. Blood donation of more than 100 mL within 30 days of planned administration of trial medication or intended blood donation during the trial
17. Intention to perform excessive physical activities within one week prior to the administration of trial medication or during the trial
18. Inability to comply with the dietary regimen of the trial site
19. A marked baseline prolongation of QT/QTc interval (such as QTc intervals that are repeatedly greater than 450 ms) or any other relevant ECG finding at screening
20. A history of additional risk factors for *Torsade de Pointes* (such as heart failure, hypokalaemia, or family history of Long QT Syndrome)
21. Subject is assessed as unsuitable for inclusion by the investigator, for instance, because the subject is not considered able to understand and comply with study requirements, or has a condition that would not allow safe participation in the study

In addition, the following trial-specific exclusion criteria apply:

22. History of relevant neurological disorder affecting the peripheral or central nervous system (this includes, but is not limited to: stroke, epilepsy, inflammatory or atrophic diseases affecting the nervous system, cluster headache or any cancer of the nervous system). Febrile seizures in childhood or adolescence, recovered carpal tunnel syndrome, recovered uncomplicated meningitis, recovered herpes zoster, tension headache, occasional benign tics (e.g. due to stress) or minor para- or dysesthesia (e.g. as a side effect of prior blood withdrawal) do not constitute a history of relevant neurological disorder.
23. History of immunological disease except allergy not relevant to the trial (such as mild hay fever or dust mite allergy) and except asthma in childhood or adolescence
24. History of cancer (other than successfully treated basal cell carcinoma)
25. Liver enzymes (ALT, AST, gGT, AP) above upper limit of normal at the screening examination

Proprietary confidential information © 2019 Boehringer Ingelheim International GmbH or one or more of its affiliated companies

26. Within 10 days prior to administration of trial medication, use of any drug that could reasonably inhibit platelet aggregation or coagulation (e.g., acetylsalicylic acid)
27. Male subjects with WOCBP partner who are unwilling to use male contraception (condom or sexual abstinence) from time point of first administration of trial medication until 30 days after the last administration of trial medication

For study restrictions, refer to Section [4.2.2](#).

### 3.3.4 Withdrawal of subjects from treatment or assessments

Subjects may discontinue trial treatment or withdraw consent to trial participation as a whole ('withdrawal of consent') with very different implications; please see Sections [3.3.4.1](#) and [3.3.4.2](#) below.

If a subject is removed from or withdraws from the trial prior to the first administration of trial medication, the data of this subject will not be entered in the case report form (CRF) and will not be reported in the clinical trial report (CTR). If a subject is removed from or withdraws from the trial after the first administration of trial medication, this will be documented and the reason for discontinuation must be recorded in the CRF; in addition, the data will be included in the CRF and will be reported in the CTR. At the time of discontinuation, a complete end of trial examination will be performed, if possible, and the information will be recorded in the CRF.

#### 3.3.4.1 Discontinuation of trial treatment

An individual subject will discontinue trial treatment if:

1. The subject wants to discontinue trial treatment, without the need to justify the decision
2. The subject has repeatedly shown to be non-compliant with important trial procedures and, in the opinion of both, the investigator and sponsor representative, is not willing or able to adhere to the trial requirements in the future.
3. The subject needs to take concomitant medication that interferes with the investigational medicinal product or other trial treatment
4. The subject can no longer receive trial treatment for medical reasons (such as surgery, adverse events [AEs], or diseases)
5. The subject has an elevation of AST and/or ALT  $\geq 2$ -fold ULN and/or needs to be followed up according to the DILI checklist provided in the ISF
6. The subject experiences a drug-related AE of severe intensity or a serious AE

In addition to these criteria, the investigator may discontinue subjects at any time based on his or her clinical judgment.

Even if the trial treatment is discontinued, the subject remains in the trial and, given his agreement, will undergo the procedures for early treatment discontinuation and follow up as outlined in the [Flow Chart](#) and Section [6.2.3](#).

Proprietary confidential information © 2019 Boehringer Ingelheim International GmbH or one or more of its affiliated companies

### **3.3.4.2 Withdrawal of consent to trial participation**

Subjects may withdraw their consent to trial participation at any time without the need to justify the decision. If a subject wants to withdraw consent, the investigator should be involved in the discussion with the subject and explain the difference between trial treatment discontinuation and withdrawal of consent to trial participation, as well as explain the options for continued follow up after trial treatment discontinuation, please see Section [3.3.4.1](#) above

### **3.3.4.3 Discontinuation of the trial by the sponsor**

Boehringer Ingelheim reserves the right to discontinue the trial at any time for any of the following reasons:

1. Failure to meet expected enrolment goals overall or at a particular trial site
2. New toxicological findings, serious adverse events, or any safety information invalidating the earlier positive benefit-risk-assessment. More specifically, the trial will be terminated if more than 50% of the subjects have drug-related and clinically relevant adverse events of moderate or severe intensity, or if at least 1 drug-related serious adverse event is reported
3. Violation of GCP or the CTP impairing the appropriate conduct of the trial-
4. The sponsor decides to discontinue the further development of the investigational product

### **3.3.5 Replacement of subjects**

In case more than 4 subjects do not complete the trial, the Clinical Trial Leader together with the Trial Pharmacokineticist and the Trial Statistician are to decide, if and how many subjects will be replaced. A replacement subject will be assigned a unique trial subject number, and will be assigned to the same treatment as the subject replaces.

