#### 6.2.2 Treatment periods

Samples for genotyping will be taken from all volunteers prior to first drug administration in period 1 (for details, see Section [5.5.1](#)).

Each subject is expected to participate in 2 treatment periods (Period 1: Days 1 to 3; Period 2: Days -7 to 3). At least 10 days will separate administrations of BI 894416 in the first and second treatment periods.

Proprietary confidential information © 2019 Boehringer Ingelheim International GmbH or one or more of its affiliated companies

On Day 1 of treatment period 1 / Day -1 of treatment period 2, study participants will be admitted to the trial site and kept under close medical surveillance for at least 24 h following BI 894416 administration. The subjects will then be allowed to leave the trial site after formal assessment and confirmation of their fitness.

In addition, on Day -7 of treatment period 2, subjects will be admitted to the trial site and kept under close medical surveillance for at least 2 h following the first rifampicin administration. The subjects will then be allowed to leave the trial site after formal assessment and confirmation of their fitness.

On all other study days, subjects will be treated in an ambulatory fashion.

For details on time points and procedures for collection of plasma and urine samples for PK analysis, refer to [Flow Chart](#) and Section [5.3.2](#).

The safety measurements performed during the treatment period are specified in Section [5.2](#) of this protocol and in the [Flow Chart](#). For details on times of all other trial procedures, refer to the [Flow Chart](#). AEs and concomitant therapy will be assessed continuously from screening until the end of trial examination.

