### Pharmacokinetics

The pharmacokinetic parameters listed in Section [2.1](#) for drug BI 894416 will be calculated according to the relevant SOP of the Sponsor ([001-MCS-36-472](#)).

Plasma concentration data and parameters of a subject will be included in the statistical pharmacokinetic (PK) analyses if they are not flagged for exclusion due to a protocol deviation relevant to the evaluation of PK (to be decided no later than in the Report Planning Meeting) or due to PK non-evaluability (as revealed during data analysis, based on the criteria specified below). Exclusion of a subject's data will be documented in the CTR.

Relevant protocol deviations may be

- Incorrect trial medication taken, i.e. the subject received at least one dose of trial medication the subject was not assigned to
- Incorrect dose of trial medication taken
- Use of restricted medications

Plasma concentrations and/or parameters of a subject will be considered as non-evaluable, if for example

- The subject experienced emesis that occurred at or before two times median  $t_{max}$  of the respective treatment (Median  $t_{max}$  is to be determined excluding the subjects experiencing emesis),
- A predose concentration of BI 894416 is  $>5\% C_{max}$  value of that subject in the respective treatment period
- Missing samples/concentration data at important phases of PK disposition curve

Plasma concentration data and parameters of a subject which is flagged for exclusion will be reported with its individual values but will not be included in the statistical analyses.

Descriptive and inferential statistics of PK parameters will be based on the PKS.

Only concentration values within the validated concentration range and actual sampling times will be used for the calculation of pharmacokinetic parameters. Concentrations used in the pharmacokinetic calculations will be in the same format provided in the bioanalytical report, (that is, to the same number of decimal places provided in the bioanalytical report).

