## **7.7 DETERMINATION OF SAMPLE SIZE**

It is planned to enter a total of 16 subjects in the trial, including up to 4 non PK evaluable subjects. The planned sample size is not based on a power calculation but is considered sufficient to achieve the aims of this exploratory trial. With this sample size, the following precision in estimating the ratio of geometric means (test/reference) can be expected with 95% probability. Precision is defined as the ratio of upper CI limit to the relative BA estimate. Note that the precision is independent of the actual ratio of geometric means.

The intra-individual coefficient of variation (gCV) was estimated from inter-individual gCV from preliminary PK data of the SRD part of a previous trial using the 54 mg dose (data on file). The observed inter-individual gCV was roughly 27% for  $AUC_{0-\infty}$  and 29% for  $AUC_{0-tz}$ . Assuming a within-subject correlation 0.8 for  $AUC_{0-\infty}$  and  $AUC_{0-tz}$ , the estimated upper 70% CI of the intra-individual gCV was roughly 17% for  $AUC_{0-\infty}$  and 15% for  $AUC_{0-tz}$ .

Assuming a gCV of 17% for BI 894416 and given a sample size of 12 subjects with evaluable data for primary analysis, the precision of the two-sided 90% confidence interval of the bioavailability ratio will be approximately 1.18 for a greater gCV of 22%, the precision would still be approximately 1.24. Table [7.7:1](#) provides an overview of the achievable precision for estimating the ratio of geometric means (test/reference). For illustrative purposes, the expected 90% confidence intervals with 95% tolerance probability are displayed for different values of the ratios T/R of geometric means.

Proprietary confidential information © 2019 Boehringer Ingelheim International GmbH or one or more of its affiliated companies

Table 7.7: 1

Precision that can be expected with 95% probability and illustrative two-sided 90% confidence intervals around the ratios of geometric means (T/R) for different gCVs in a one-way crossover trial ( $N=12$ )

gCV [%]	Precision upper CL / relative BA estimate	Ratio [%]*	Lower CL [%]	Upper CL [%]
12	1.12	100	88.94	112.44
12	1.12	150	133.41	168.66
12	1.12	200	177.87	224.88
12	1.12	400	355.75	449.76
17	1.18	100	84.75	118.00
17	1.18	150	127.12	177.00
17	1.18	200	169.49	236.00
17	1.18	400	338.99	472.00
22	1.24	100	80.80	123.76
22	1.24	150	121.20	185.64
22	1.24	200	161.60	247.52
22	1.24	400	323.21	495.04

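### Should the replacement rule count PK-evaluable subjects, as the sample-size section does, rather than subjects who complete the trial?

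*Protocol*

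**What the plan says.** Section 3.3.5 of the protocol sets the trigger: "In case more than 4 subjects do not complete the trial", the Clinical Trial Leader, the Trial Pharmacokineticist and the Trial Statistician decide whether to replace anyone, and how many.

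Section 7.7 sets the allowance: "It is planned to enter a total of 16 subjects in the trial, including up to 4 non PK evaluable subjects". The precision statement is made "given a sample size of 12 subjects with evaluable data for primary analysis". The same section says that the sample size does not come from a power calculation and calls the trial exploratory.

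Section 7.3, under Pharmacokinetics, lists reasons why a profile may be unusable: early emesis, a pre-dose concentration above 5% of Cmax, or "Missing samples/concentration data at important phases of PK disposition curve". Data may be excluded "due to PK non-evaluability (as revealed during data analysis, based on the criteria specified below").

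On subjects who stop treatment, Section 3.3.4.1 says "Even if the trial treatment is discontinued, the subject remains in the trial", while Section 6.2.2 says "Each subject is expected to participate in 2 treatment periods". Section 3.1 adds that "it is acceptable to treat all subjects entered in this trial in a single cohort".

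The SAP announces no change to the planned analysis (Section 4) and repeats the protocol's analysis sets (Section 6.3). Section 7.8 describes treated subjects who do not finish as dropouts or withdrawals.

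**The concern.** The two sections share a number but count different things. Section 7.7 tolerates 4 subjects without evaluable PK; Section 3.3.5 reacts to a fifth subject who does not complete. None of the non-evaluability reasons in Section 7.3 requires a subject to leave, so someone can attend every visit and still give no usable pair. Four non-completers and one completer who vomits early would leave 11 pairs with the rule silent.

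The term for completing is also not formally defined. Read alone, Section 3.3.4.1 might let a subject who stops during rifampicin pre-treatment pass as still in the trial, although he has no test profile. The pharmacokinetic set would not expose the shortfall, because it admits a subject with a single value from one period.

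Precision is the only quantitative support for the sample size. If the replacement rule is meant to protect it, the rule watches the wrong count, and the confidence intervals for AUC0-∞ and Cmax could be wider than Section 7.7 indicates.

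**Working it through.** **Inputs (Protocol Section 7.7 and Table 7.7:1).** Enrolment 16; allowance 4; evaluable n = 16 − 4 = 12; gCV 12%, 17% or 22%; two-sided 90% interval; 95% tolerance probability; precision = upper limit divided by point estimate.

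**Formula for n complete reference-test pairs.**

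- σ = √ln(1 + gCV²)
- log half-width w = t(0.95; n−1) × σ × √(2/n) × √[χ²(0.95; n−1)/(n−1)]
- precision = exp(w)

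**Reproducing the plan, n = 12, gCV 17%.** σ = √ln(1.0289) = 0.1688; t = 1.7959; √(2/12) = 0.4082; √(19.675/11) = 1.3374.

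w = 1.7959 × 0.1688 × 0.4082 × 1.3374 = 0.1655, so precision = 1.180. At a ratio of 100% the limits are 84.75 and 118.00, as in Table 7.7:1. The 12% and 22% rows also reproduce (1.1244 and 1.2376). Using n = 16 gives 1.1446 at 17%, which does not match. The stated precision therefore rests on 12 complete pairs.

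**Falling below 12 with the rule silent.** Take 4 non-completers plus 1 or 2 completers without an evaluable pair.

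- n = 11: t = 1.8125; √(2/11) = 0.4264; √(18.307/10) = 1.3530. At 17%, w = 0.1765.
- n = 10: t = 1.8331; √(2/10) = 0.4472; √(16.919/9) = 1.3711. At 17%, w = 0.1897.

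| Pairs | Precision, gCV 17% | Precision, gCV 22% | w relative to 12 pairs |
|---|---|---|---|
| 12 | 1.180 | 1.238 | 1.000 |
| 11 | 1.193 | 1.255 | 1.066 |
| 10 | 1.209 | 1.277 | 1.146 |

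At a ratio of 100%, 10 pairs give 82.72 to 120.89% at gCV 17% (planned 84.75 to 118.00%) and 78.32 to 127.68% at gCV 22% (planned 80.80 to 123.76%). Subjects with one usable period get no weight here.

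**How likely.** The documents give no loss rates. Purely as an assumption, let each of 16 subjects fail to complete with probability 5 to 15% and each completer be non-evaluable with probability 2 to 10%, independently. The chance of at most 4 non-completers together with fewer than 12 pairs then runs from 0.3% to 23.7%, with 5.3% at 10% and 5%. The range is that wide because the rates are guesses.

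**Who counts as a non-completer.** Section 3.3.4.1 keeps a subject who stops treatment in the trial for early-discontinuation and follow-up procedures. Section 6.2.3 sends him to the end-of-trial visit. Section 6.2.2 expects two periods. Section 8.3.1 contrasts completing participation with premature discontinuation, and SAP Section 7.8 equates not finishing with dropping out or withdrawing. Read together, a subject who stops before BI 894416 in Period 2 is a non-completer. What remains is the completer with unusable PK.

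**The case for a change.** The strongest case for a change is that one sentence would tie the trigger to the quantity Section 7.7 relies on. The roles that judge evaluability already sit in the decision, and early emesis, missed key samples and stopped treatment are all known during conduct. At gCV 22% both shortfall cases exceed the value of about 1.24 that Section 7.7 presents as still achievable. These points stand: the counts differ, and some non-evaluable completers could be recognised in time.

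They do not carry a change, for three reasons.

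- Section 3.3.5 never guaranteed 12 pairs. Even when triggered, the team may replace nobody. The wording affects when three people must confer, not the number analysed.
- Non-completion is visible while replacement is still practical. Some non-evaluability emerges only at data analysis, and relevant deviations need be settled only by the Report Planning Meeting. An observable count is a reasonable operational trigger. A count of subjects known or expected to be non-evaluable replaces it with a judgement and still misses late losses.
- A trigger requiring both primary endpoints in both periods would bring its own mismatch. Parameters are excluded and modelled individually, so a subject without AUC0-∞ may still give a Cmax pair, and the rule could fire while Cmax has 12 pairs or more.

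The practical effect of a stricter trigger would be earlier discussion and possibly a further dosing round after a planned single cohort.

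**Conclusion.** No change is needed. The mismatch is a wording gap that the three named roles can handle sensibly, and nothing stops them discussing PK losses they already know of.

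In the cases examined the log half-width grows by 6.6% (11 pairs) or 14.6% (10 pairs). At gCV 17%, even 10 pairs (1.209) stay inside the 1.24 that the protocol shows for its less favourable gCV; at 22% they do not (1.277). The cost is width alone: the test/reference ratio is not biased by a shortfall in numbers as such, and the interval is computed from the data obtained. Section 7.2 sets no hypothesis test or acceptance range, so no decision threshold is crossed.

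This rests on the protocol's gCVs of 17% and 22%, on a shortfall of one or two pairs beyond 4 non-completers, and on losses unrelated to the size of the interaction. A larger shortfall would cost more (8 pairs give 1.254 at gCV 17%), but that needs 4 non-completers and 4 non-evaluable completers, or some other combination of 8 losses among 16 with no more than 4 non-completers. The documents give no loss rate that would make this a planning case.
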